## 9.7. Overdose of Study Intervention

Study medication overdose (rivaroxaban and placebo) including misuse or abuse of the product and medication errors, should be reported to the study investigator immediately and reported in the clinician notes and the eCRF.

An approved reversal agent for rivaroxaban is andexanet alfa. Its use will be based on the clinical judgement of the treating physician.

## 9.8. Pregnancy

The investigator or designee will be required to inquire about pregnancy at screening and every study visit but pregnancy testing will not be required.

Pregnancies occurring in participants enrolled in this study must be reported, and details collected including outcome of the pregnancy.

If pregnancy is reported, the participant should be withdrawn from study treatment but continue to be followed for safety. Details of the pregnancy as well as outcome should be followed and recorded.

Pregnancy alone is not regarded as an AE unless there is a possibility that the study IP may have interfered with the effectiveness of a contraceptive medication. Elective abortions without complications should not be considered AEs unless they were therapeutic abortions.

Hospitalization for normal delivery of a healthy newborn should not be considered an SAE.

Pregnancy is not considered an SAE unless there is an associated abnormal pregnancy outcome (e.g. spontaneous abortion, fetal death, stillbirth, congenital anomalies, ectopic pregnancy).

Any abnormal pregnancy outcomes during the study (e.g. spontaneous abortion, fetal death, stillbirth, congenital anomalies, ectopic pregnancy) should be reported as an SAE.

#### **9.8.1. Contraceptive Guidance**

Women with history of hysterectomy, bilateral salpingectomy or bilateral oophorectomy are not considered females of childbearing potential.

Women physically capable of pregnancy must agree to use adequate contraception during the study. Examples include:

- abstinence from penile-vaginal intercourse, when this is their preferred and usual lifestyle
- oral contraceptives, either combined or progestogen alone
- injectable progestogen
- implants of etonogestrel or levonorgestrel
- estrogenic vaginal ring
- percutaneous contraceptive patches
- intrauterine device or intrauterine system
- male partner sterilization prior to the female participant's entry into the study, and this male is the sole partner for that participant
- male condom combined with a vaginal spermicide (foam, gel, film, cream or suppository),
- male condom combined with a female diaphragm, either with or without a vaginal spermicide (foam, gel, film, cream, or suppository).

Adequate contraception does not apply to participants of child-bearing potential with same sex partners, when this is their preferred and usual lifestyle.

#### **9.9. Biohazard Containment**

All dangerous goods and materials, including diagnostic specimens and infectious substances, will be handled and transported based on requirements of relevant local regulatory authorities.

## 10. Statistical Considerations

### 10.1. Sample Size Determination

#### Efficacy

The total number of participants planned to be enrolled is approximately 600 (300 per group). If the true control rate for progression to moderate or severe category or greater is at least 30%, 294 participants per group will result in 80% power when the true Study Intervention effect is 35%. This sample size assumes a drop-out rate of 10% and a 1-sided Type I error rate of 2.5%.

#### Safety

With 300 participants in the rivaroxaban intervention group, there is 80% probability to observe at least one SAE related to rivaroxaban when the true SAE rate is at least 0.54%.

### 10.2. Statistical Hypothesis

Primary Hypothesis: Treatment with the DOAC rivaroxaban will reduce progression to moderate or severe disease category or higher (Gates MRI ordinal scale  $\geq 3$ ) relative to placebo in high risk participants with mild COVID-19.

### 10.3. Populations for Analyses

For the purposes of analysis, populations are defined in [Table 9](#).

**Table 9: Populations for Analysis**

Population	Description
Intention to treat (ITT) population	All participants randomly assigned to study intervention. Participants will be analyzed according to the intervention to which they were randomized.
Modified intention to treat (mITT) populations	All participants randomly assigned to study intervention, who received the study intervention and have mild disease at study entry. Participants will be analyzed according to the intervention they actually received.
Per Protocol (PP) population	All participants randomly assigned to study intervention, who received the study interventions as planned, have mild disease at study entry, and did not substantially deviate from the protocol procedures. Participants will be analyzed according to the intervention they actually received.
Safety population	All participants randomly assigned to study intervention, who received the study intervention. Participants will be analyzed according to the intervention they actually received.

### **10.3.1. Assigning Shared Controls across Multiple Intervention-Specific Analysis Populations**

Each intervention may be initiated and stopped at different time frames, and within different sites. Depending on the number of interventions that a participant can be eligible to receive, a participant randomized to a control arm may be part of multiple intervention-specific analysis populations for the purposes of comparing a single intervention to control. We note the following core principles associated with sharing controls across intervention-specific analysis populations:

[figure not shown]
- Controls will only be shared across multiple intervention-specific populations when there is randomization across those interventions and the control. All participants will only be randomized once.
- A participant who is eligible for multiple interventions at a site will be randomized equally to receive one of the interventions for which they are eligible vs control. Participants randomized to control will be equally likely to receive the matched control of each intervention for which they are eligible. If the participant is randomized to control, they will be assigned to each of the intervention-specific analysis populations included in the randomization. A participant randomized to control will not be assigned to an intervention-specific analysis population that was not included in the randomization.
- Controls will only be shared contemporaneously. A participant can only be used in the intervention-specific population(s) that were available and included at the time of their randomization.
- A control does not have to receive the intervention-specific matched control to be eligible for an intervention-specific population. For example, a participant randomized 1:1:1 to receive two available interventions vs control would serve as a control for each of the interventions even if randomized to the matched control of the first interventions. The primary comparison will utilize eligible participants in the control arm with all control formulations.

The randomization strategy for up to 3 contemporaneously available interventions is shown in [Figure 3](#). Strategies for 2 interventions and for 1 intervention are shown in [Figure 4](#) and [Figure 5](#), respectively.

[figure not shown]
This randomization strategy can easily be generalized beyond 3 contemporaneously available interventions and will ensure approximately equal randomization of each intervention to control, while helping to maintain blinding and minimize possible bias.

Participants randomized to rivaroxaban or control under the principles listed above will be assigned to the rivaroxaban-specific analysis population.

[figure not shown]
**Figure 3: Randomization strategy for sites where 3 interventions are being studied**

**Figure 4: Randomization strategy for sites where 2 interventions are being studied**

**Figure 5: Randomization strategy for sites where only 1 intervention is being studied**

#### 10.4. Primary and Key Secondary Endpoints

The primary efficacy endpoint is the proportion of participants who progress to moderate or severe disease category or higher (Gates MRI ordinal scale  $\geq 3$ ) through Day 28.

Secondary efficacy endpoints include time to disease resolution, defined as symptoms resolution with or without viral clearance, proportion of participants with disease resolution, Gates MRI and WHO ordinal scales, and incidence and duration of hospitalization.

Primary safety endpoints include the frequency of Grade 3 and Grade 4 AEs, AEs resulting in study intervention discontinuation and SAEs.

## 10.5. Statistical Methods

The statistical analysis plan will be developed and finalized before database lock and will describe the detailed analytical plans and procedures for the interim and final analyses, and accounting for missing data.

### 10.5.1. Efficacy Analyses

#### **Primary efficacy endpoints**

The primary efficacy analysis will be conducted in the ITT population. Within the rivaroxaban analysis population as defined in [Section 10.3.1](#), participants randomized to rivaroxaban will be compared to participants randomized to placebo/standard of care.

The proportion of participants who progress to moderate or severe disease category or greater through Day 28 will be summarized by treatment group. The absolute difference in the risk of progression to moderate or severe disease category or greater will be assessed using the stratified Miettinen and Nurminen method to compare the difference between two rates [[Miettinen 1985](#)].

Sensitivity analyses will be repeated as described above using the mITT and PP populations, to assess the robustness of the primary results.

#### **Secondary endpoints**

Secondary analyses will primarily be conducted in the ITT population, with sensitivity analyses performed in the mITT and PP populations. Specific details of each analysis will be provided in the SAP.

For time to disease resolution endpoints, a stratified Log-rank test will be used. A stratified Cox PH model will be used to estimate the hazard ratios and corresponding CIs associated with the rate of disease resolution for the study intervention relative to control. Due to anticipated heterogeneity in the rate of disease resolution, pre-specified baseline variables, including age, BMI, and days of symptoms at time of enrollment may be included in the model to increase precision. The appropriateness of the proportional hazard ratio assumption will be assessed.

The proportion of participants who achieve disease resolution at each time point through Day 28 will be summarized by treatment group with 95% exact CIs. Differences in the proportion of participants achieving disease resolution between each intervention and control will be assessed using the stratified Miettinen and Nurminen method to compare the difference between two rates [[Miettinen 1985](#)].

The distributions of the Gates MRI scale score and WHO ordinal score will be summarized by day and treatment group. The overall burden of disease for an individual participant may be calculated as the area under the curve over time. Differences in disease scores will be assessed using a linear model assessing the impact of treatment on disease burden, while controlling for baseline disease burden, age, BMI, and days of symptoms at time of enrollment. Differences in disease severity at key timepoints (e.g., Day 14) will also be assessed using a proportional odds model.

The proportion of hospitalized participants will be summarized by treatment group with 95% exact CIs. The relative risk of hospitalization for patients randomized to each intervention relative to control will be assessed using a stratified analysis for the comparison of two rates.

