## **9.2. Procedures at Visits from Day 4 through Day 28**

At each of these visits on Days 4, 6, 8, 10, 12, 14, 18, 21, 24, 28, the study staff conducting the visit will:

- Introduce themselves, explain their role to the participant, and confirm the identity of the participant
- Confirm that the means of contact is adequate to conduct the contact/visit
- Collect information on COVID-19 symptoms and signs
- Assess the Gates MRI and WHO ordinal scales
- Collect information on AEs
- Collect information on bleeding events and severity
- Collect information on concomitant medications
- Remind the participant to take the dose daily through Day 21, and not to show the study IP tablets or describe the tablets detailed appearance, to maintain the masking of the study staff.
- Collect information on adherence to study IP and any dosing error (if applicable)
- Ask participant to collect temperature, and oxygen saturation during the encounter (study staff will document temperature and oxygen saturation)
- Ask participant to collect nasal sample during the encounter for Days 4, 8, 14, 21 and 28
- Inquire about pregnancy, as appropriate.

As needed, additional contact with the study clinician or staff will be conducted at the request of the participant (e.g., if developing concerning symptoms or an AE).

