### **9.6. Assessment of COVID-19 Signs and Symptoms**

COVID-19 signs and symptoms reported to the study staff to be recorded in the CRF/eCRF are shown in [Table 6](#). Other symptoms or signs considered by the PI to be related to COVID-19 can be added as necessary. Of note, anosmia and ageusia will be collected but not included in the symptom endpoint analysis as they may be long-lasting despite resolution of other symptoms (possibly due to direct viral damage of the olfactory and gustatory receptors). Therefore, their continued presence post therapy may not be indicative of a poor response to study intervention(s).

The PI or designee will query the participants about the symptoms listed below and determine symptom resolution (yes or no) since their last visit.

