11.2.1 Estimand

The treatment policy estimand with respect to the secondary efficacy objective is defined for the key secondary endpoints by the following:

Population: Participants in the ITT population.

Patient-level outcome: Time to disease resolution through day 28.

Intercurrent events: The following intercurrent events to be taken into account:

1. If a death occurs prior to Day 28, the participant will be considered as not having disease resolution through Day 28 (i.e., censored at Day 28).
2. If a participant is lost to follow-up prior to Day 28, the participant will be considered as not having disease resolution and will be censored at the time of lost to follow-up.
3. If a participant discontinues the study [for any reason: lost to follow-up, progression to moderate or severe COVID-19 (or worse), withdrawal of consent] prior to initiation of IP dosing on Day 1 and no symptoms resolution assessment is available, the participant will be considered as not having disease resolution and will be censored on Day 1.

Participants who discontinue study intervention will be followed at least until end of study, Day 35.

Population-level summary measure: Median time to disease resolution.

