11.2.2 Disease Resolution

11.2.2.1 Time to Disease Resolution (Symptoms Resolution)

Disease resolution is defined as symptoms resolution (new onset coronavirus disease 2019 (COVID-19) symptoms resolved, and pre-existing symptoms returned to baseline) through Day 28. For the time to disease resolution analysis, the following hypothesis will be tested: prophylactic treatment with rivaroxaban will increase the rate of time to disease resolution relative to placebo in high risk participants with mild COVID-19.

Time to disease resolution is defined as the time from first dose to the date of symptoms resolution (as determined by the investigator: has the participant’s COVID-19 signs and/or symptoms resolved or returned to baseline). The following rules (Table 3) will be used to define time to disease resolution:

Table 3: Censoring rules for time to disease resolution.

| Situation | Outcome | Date of event/censoring |
|---|----------|--|
| Death for any reason | Censored | Day 28 |
| Discontinued prior to Day 28 without disease resolution | Censored | Date of last disease resolution assessment |
| No disease resolution through Day 28 | Censored | Day 28 |
| Randomized, treated but no post-baseline assessments available | Censored | Day 1 |
| Disease resolution through Day 28 | Event | Initial date of last sequence of consecutive disease resolution. |
| Discontinued prior to Day 28 with disease resolution at last assessment | Event | Initial date of last sequence of consecutive disease resolution. |
| Randomized, not treated | Censored | Date of randomization |

*sequence = a series of one or more disease resolutions with no progression.

Example scenarios are included in Table 4 for reference.

Table 4: Example scenarios for time to time to disease resolution.

| Time point | Day 1 | Day 4 | Day 6 | Day 8 | Day 10 | Day 12 | Day 14 | Day 18 | Day 21 | Day 24 | Day 28 | Endpoint |
|----------------|-------|-------|-------|-------|--------|--------|--------|--------|--------|--------|--------|-----------------------------|
| Participant 1 | N | N | N | N | N | N | N | N | N | N | N | No DR, censored at Day 28 |
| Participant 2 | N | Y | N | N | N | N | Died | | | | | No DR, censored at Day 28 |
| Participant 3 | N | Y | Y | N | N | N | Disc. | | | | | No DR, censored at Day 12 |
| Participant 4 | N | Y | N | N | N | Y | Y | Y | Y | Y | N | DR at Day 12* |
| Participant 5 | N | Y | Y | N | N | Y | Y | Y | Disc. | | | DR at Day 12 |

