| Participant 6 | N | N | Y | Y | N | N | Y | Y | Y | Y | Y | DR at Day 14 |
| Participant 7 | N | N | N | N | N | N | N | N | N | N | Y | DR at Day 28 |
| Participant 8 | N | N | N | N | N | Y | Y | Y | Y | N | N | No DR, censored at Day 28** |
| Participant 9 | N | Y | NA | NA | NA | NA | NA | NA | NA | NA | NA | DR at Day 4 |
| Participant 10 | N | NA | NA | NA | NA | NA | NA | NA | NA | NA | NA | No DR, censored at Day 1 |
| Participant 11 | Y | Y | Y | Y | Y | Y | Y | Y | Y | Y | Y | DR at Day 1 |
| Participant 12 | N | Y | N | N | N | Y | Y | N | Disc. | | | No DR, censored at Day 18 |

* Due to consecutive days with disease resolution and followed by a day with no disease resolution as the last assessment.

**Due to consecutive days with no disease resolution occur after days with disease resolution.

DR = disease resolution. N=no; Y=yes. NA=Not available.

For time to disease resolution, a stratified 1-sided log-rank test, stratified by number of days since onset of symptoms at time of randomization (<6 days or ≥6 days), will be used to compare between the study intervention and control. The Kaplan-Meier method will be used to obtain the estimates of medians with the associated 2-sided 95% CIs of time to disease resolution,

computed using Brookmeyer and Crowley method. A stratified Cox proportional hazards model, stratified by number of days since onset of symptoms at time of randomization (<6 days or ≥ 6 days) will be used to estimate the hazard ratio and the corresponding 2-sided 95% CI associated with the rate of disease resolution for the study intervention relative to control.

Due to anticipated heterogeneity in the rate of disease resolution, pre-specified baseline variables, including age and BMI will be included in the model to increase precision. Including time-dependent variables, i.e., log(time)-by-variables interactions, to the model to fit a stratified Cox non-proportional hazards model to assess the proportional hazards assumption. If the coefficients for the time-dependent variables are not statistically different from zero based on a chi-square test with 1 degree of freedom would suggest that proportional hazards assumption is adequate for all variables included in the model.

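### Time to resolution is known only to the visit (2–4 days apart; swabs 3–7) but analysed as an exact date, so medians run late, arm differences can be hidden or inflated, and the hazard ratio depends on an unstated tie rule

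*Protocol*

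**What the plan says.** **Observation.** Under Protocol 9.6 the PI or designee is to "determine symptom resolution (yes or no) since their last visit". Protocol 9.2 sets the occasions: "At each of these visits on Days 4, 6, 8, 10, 12, 14, 18, 21, 24, 28". Swabs are sparser: "Ask participant to collect nasal sample during the encounter for Days 4, 8, 14, 21 and 28".

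**Dating.** SAP 11.2.2.1 states: "Time to disease resolution is defined as the time from first dose to the date of symptoms resolution". Its Table 3 fixes the event date as "Initial date of last sequence of consecutive disease resolution". In Table 4, Participant 6 is unresolved on Day 12 and resolved on Day 14, and is scored as an event on Day 14. Every example in that table falls on a visit day.

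**Analysis.** The estimand in SAP 11.2.1 names its target: "Population-level summary measure: Median time to disease resolution". SAP 11.2.2.1 adds: "The Kaplan-Meier method will be used to obtain the estimates of medians". For the hazard ratio, Protocol 10.5.1 states: "A stratified Cox PH model will be used to estimate the hazard ratios and corresponding CIs associated with the rate of disease resolution". SAP 11.2.2.1 also plans a one-sided stratified log-rank test and a stratified Cox model with age and BMI. SAP 11.2.2.2 treats the composite (symptoms plus two consecutive negative tests) in a similar way.

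Neither document mentions interval censoring, grouped time or ties. SAP Appendix 4 is headed SAS Code, but no code appears in the available text.

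**The concern.** What is known for Participant 6 is that resolution came after Day 12 and by Day 14. Recording Day 14 as exact makes every event late by an unknown part of the gap and piles events onto a few shared days. The median is the stated summary measure of a key secondary endpoint. Apart from off-schedule visits it can only be a visit day, and a larger sample does not change that. With this many ties, the Cox estimate also depends on the tie method, which should be fixed in advance.

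**Working it through.** **Inputs.** The schedules, dating rule and methods are as above. The documents give no median, hazard ratio (HR) or power for this endpoint, so there is no plan figure to reproduce. The medians, HRs and Weibull shapes below are assumptions. Times are days after first dose (study day minus 1):
- symptom grid 3, 5, 7, 9, 11, 13, 17, 20, 23, 27
- swab grid 3, 7, 13, 20, 27

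**1. Lateness of the median.** A true median falling anywhere in a gap of length g is on average g/2 late. For medians spread evenly over 5 to 20 days:
- Symptoms: four gaps of 2, one of 4, one of 3. (4×2² + 4² + 3²)/2 = 20.5; 20.5/15 = 1.4 days, maximum just under 4. At most 2 days late over (8 + 2 + 2)/15 = 80% of the range.
- Swabs: the last 2 days of one gap, then gaps of 6 and 7. (2² + 6² + 7²)/2 = 44.5; 44.5/15 = 3.0 days, maximum just under 7.

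A sweep in steps of 0.05 day gives 1.3 and 2.9.

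**2. Difference between medians.**
- Hidden: true 16.5 vs 13.2 days (HR 1.25, shape 1). Both lie between 13 and 17, so both read Day 18, and 3.3 days becomes 0.
- Inflated: true 15.0 vs 12.9 (HR 1.25, shape 1.5). They read Day 18 vs Day 14, so 2.1 days becomes 4. On the swab grid they read Day 21 vs Day 14, a 7-day difference.
- How often the two visit medians coincide (shape 1.5, control median 5–20 days): symptoms 35% at HR 1.25 and 3% at HR 1.5; swabs 79% and 59%.

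**3. Hazard ratio.** Take one gap with cumulative hazard H in control and HR×H on treatment, and equal numbers at risk. Breslow estimates the ratio of gap risks, (1 − e^(−HR·H))/(1 − e^(−H)). For the first symptom gap, control median 8 days, shape 1.2, HR 1.3:
- H = 0.693×(3/8)^1.2 = 0.2136, so control risk = 0.1923
- 1.3×H = 0.2777, so treated risk = 0.2425
- ratio 1.261; log 0.2316 against log 1.3 = 0.2624, a shrinkage of 11.7%
- the complementary log-log contrast returns 0.2777/0.2136 = 1.30

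Large-sample Cox estimates over the full schedule (true HR 1.3, shape 1.2, 1:1, unstratified):

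| Grid | Control median | Breslow HR | log HR lost | Efron HR | log HR lost |
|---|---|---|---|---|---|
| Symptom | 8 | 1.254 | 13.8% | 1.297 | 0.8% |
| Symptom | 12 | 1.268 | 9.6% | 1.299 | 0.4% |
| Symptom | 16 | 1.275 | 7.3% | 1.299 | 0.2% |
| Swab only | 8 | 1.214 | 26.1% | 1.288 | 3.5% |
| Swab only | 12 | 1.237 | 19.1% | 1.294 | 1.7% |
| Swab only | 16 | 1.251 | 14.7% | 1.297 | 0.9% |

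Simulation at 300 per arm gave matching Breslow ranges, 7–14% and 15–25%. Earlier, steeper resolution is worse. At true HR 1.5, shape 2, control median 6, Breslow gives 1.36 (symptoms) and 1.24 (swabs); Efron gives 1.48 and 1.39.

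In simulation on the symptom grid (shape 1, control median 8), exact-time / Breslow / Efron / grouped-time estimates were 1.270 / 1.233 / 1.267 / 1.270 at true HR 1.25 and 1.492 / 1.415 / 1.488 / 1.494 at 1.5.

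**4. The planned test.** Unstratified log-rank power (300 per arm, HR 1.3, shape 1.2, control median 8/12/16, 200 runs, standard error about 0.03): exact dates 0.85/0.83/0.79; symptom grid 0.86/0.83/0.80; swab grid 0.84/0.81/0.80.

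**The case against.** Several points on the other side stand.

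- **Power.** A reader might infer that visit dating costs the trial power. Rejection based on a Breslow Cox model does fall, but the planned test is the log-rank, and step 4 shows no material loss. Both arms share the schedule, so the test is also valid under no effect.
- **Vanishing differences.** A reader might infer that real median differences disappear. They can, but they can equally be inflated. On the symptom schedule at HR 1.5 the two medians rarely coincide.
- **Composite grid.** The composite needs both components, so it falls on a symptom visit when symptoms resolve last. With independent components, roughly a quarter of events fell off the swab days. Extra swabs are also allowed. The swab-only figures are therefore an upper range.
- **Event days.** Table 4 allows an event on Day 1 (Participant 11). SAP 9.7 generally applies no visit windows, so off-schedule visits will spread the dates a little.
- **Possible dates or code.** The SAP speaks of a date of symptom resolution, so the eCRF might hold one, and the SAS appendix might name a tie option. Neither can be ruled out. However, Table 4 works only with visit days, and the text should settle both points.
- **Interval-censored median.** A Turnbull estimate cannot restore a difference when both medians lie in one visit gap.
- **Existing cover.** SAP 11.2.3 compares proportions resolved by Days 8, 14, 21 and 28, which needs no exact dates.

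**Conclusion.** The point holds for estimation. Visit-dated medians run late by about 1 to 2 days for symptoms and up to several days for the composite, and their difference is unreliable in either direction. The hazard ratio is biased toward 1 by a material amount only if Breslow ties are used: about 7–14% of the log HR for symptoms, and about 15–26% as an upper range for the composite. With Efron ties the symptom bias is about 1% or less under the base assumptions; on swabs it grows when resolution is early and steep.

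These sizes assume HR 1.3, Weibull shape 1.2 and control medians 8 to 16 days after first dose. Early stopping leaves fewer than 300 per arm, which affects precision but not these biases.

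The documents do not support a claim that the log-rank test is invalid or weakened, or that the primary endpoint or its sample size is affected. This is a low-cost improvement to a key secondary analysis.

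**What to change.** In SAP 11.2.2.1 and 11.2.2.2:

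1. Keep the stratified log-rank test.
2. Estimate the hazard ratio with a grouped-time proportional hazards model: complementary log-log link, visit-interval effects, treatment, symptom-duration stratum, age and BMI. At minimum, specify Efron or exact ties in the Cox model.
3. Define each event interval as running from the last unresolved visit before the final resolved run, under the Table 3 and 4 rule, to the first visit of that run. Participant 4 becomes (Day 10, Day 12] and Participant 6 (Day 12, Day 14]. Missed visits widen the interval. Add a rule for anyone already resolved on Day 1.
4. Report the median as that visit interval, or label it as the visit by which half had resolved. Use the fixed-day proportions in SAP 11.2.3 for the size of the difference, noting that they count resolution at any time up to the day, not the final resolved run.
5. State whether the first or the second negative swab dates viral clearance. Late in follow-up the choice moves the clearance date by 7 days (Day 14 vs 21, or 21 vs 28).
6. State whether the eCRF holds a resolution date and, if so, whether it is used.

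The cost is SAP wording and modest programming before database lock, with no new data. The output is slightly less familiar than a single median day.
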